- An Open-Label Extension (OLE) Year 1 Period. After completion of the 52-week randomized treatment period patients will enter the OLE period and will receive volanesorsen for 52 weeks. Assessments and study visits will be generally similar to the randomized treatment period.
- OLE Year 2 Period. Following the Week 52 visit of the OLE period, patients will have the option of continuing dosing for up to an additional 52 weeks, for a total of up to 2 years (104 weeks) of open label dosing following the 1 year (52 weeks) randomized phase. The schedule of procedures will follow the same schedule as the first year of the OLE.
- A 13-week Post-treatment Evaluation Period. Patients who do not enter the option for additional dosing in the OLE post-treatment period will go straight to a 13-week post-treatment follow-up period after completion of the first 52 weeks or after discontinuing treatment during the first 52 weeks of the OLE. Patients who enter the OLE post-treatment period will go straight to a 13-week post-treatment follow-up period after completion of the Week 104 OLE or after discontinuing treatment prior to Week 104 of the OLE.

The primary endpoint for the study will be evaluated after the last patient has completed the Week 52/ET (Early Termination) visit of the Randomized Treatment Period and will be based on the percent change from Baseline in fasting triglyceride at the primary analysis time point (Month 3).

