Lipid (triglyceride and non-triglyceride), hepatic fat fraction, and HbA1c data will be mapped to analysis visit as specified in [Appendix B](#). Assessments collected during randomized treatment period, will have analysis visit assigned according to the days relative to first dose date of randomized treatment period. Assessments collected during OLE period will have analysis visit assigned according to the days relative to first dose date of OLE period. The intent of these analysis visit windows is not to align with those prescribed for visit scheduling in the clinical study protocol but, rather, based on the protocol-defined target study day, to delineate mutually exclusive windows so that all efficacy assessments proximal to a particular study week can be integrated to best represent the patient's status during that period of the study. If a patient discontinued early from the treatment period but attended applicable landmark visits at Weeks 12, 13, 25, and etc. to collect lipid assessments, then those assessments collected at ET visit and during post-treatment follow-up period should be mapped to analysis visits as well, excluding assessment beyond 28 days after last dose of study medication. For the hepatic fat fraction and HbA1c data, data collected within the analysis visit window defined in [Appendix B](#) will be used. If there are multiple assessments within a visit window, only scheduled visit will be used, and the average will be used if there are multiple scheduled assessments, or the worst will be used if categorical result is collected in multiple scheduled assessments. If the assessments are all unscheduled, the visit nearest the scheduled date will be used, unless 2 visits are equally near, in which case the average will be used, or the worst will be used if categorical result is collected.

For efficacy data, local lab data will not be used unless central lab assessments are not available at certain visit. When calculating the baseline and analysis endpoints, only if the data from central lab is missing, then the local lab data will be utilized.

Safety assessments will be summarized by the nominal visit as collected in CRF. Multiple results with the same nominal visit will be averaged.

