**OLE Month 3 analysis time point** is at the end of OLE Month 3. For fasting lipid measurements, value at OLE Month 3 is defined as the average of OLE Week 12 (OLE Day 78) and OLE Week 13 (OLE Day 85) fasting lipid measurements. If one visit is missing, then the other visit will be used. If both visits are missing, then the value will be set as missing. .

**OLE Month 6 analysis time point** is at the end of OLE Month 6. For fasting lipid assessments, value at OLE Month 6 is defined as the average of OLE Week 25 (OLE Day 169) and OLE Week 26 (OLE Day 176) fasting assessments. If one visit is missing, then the other visit will be used. If both visits are missing, then value will be set as missing. .

**OLE Month 12 analysis time point** is at the end of OLE Month 12. For fasting lipid assessments, value at OLE Month 12 is defined as the average of OLE Week 50 (OLE Day 344) and OLE Week 52 (OLE Day 358) fasting assessments. If one visit is missing, then the other visit will be used. If both visits are missing, then the value will be set as missing. .

**OLE Month 15 analysis time point** is at the end of OLE Month 15. For fasting lipid assessments, value at OLE Month 15 is defined as the average of OLE Week 64 (OLE Day 442) and OLE Week 65 (OLE Day 449) fasting assessments. If one visit is missing, then the other visit will be used. If both visits are missing, then the value will be set as missing. .

**OLE Month 18 analysis time point** is at the end of OLE Month 18. For fasting lipid assessments, value at OLE Month 18 is defined as the average of OLE Week 77 (OLE Day 533) and OLE Week 78 (OLE Day 540) fasting assessments. If one visit is missing, then the other visit will be used. If both visits are missing, then the value will be set as missing. .

**OLE Month 24 analysis time point** is at the end of OLE Month 24. For fasting lipid assessments, value at OLE Month 24 is defined as the average of OLE Week 102 (OLE Day 708) and OLE Week 104 (OLE Day 722) fasting assessments. If one visit is missing, then the other visit will be used. If both visits are missing, then the value will be set as missing. .

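### The OLE Week 52 lipid window in SAP Appendix B has no upper limit and overlaps all 12 OLE year-2 windows, so OLE Week 52 and Month 12 lipid summaries can take in year-2 values

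*SAP*

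**What the plan says.** SAP 3.2.1 sets four rules that matter here.

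- The purpose of the windows is "to delineate mutually exclusive windows so that all efficacy assessments proximal to a particular study week can be integrated".
- The clock is common to the whole extension: "Assessments collected during OLE period will have analysis visit assigned according to the days relative to first dose date of OLE period".
- When several assessments fall in one window, "only scheduled visit will be used, and the average will be used if there are multiple scheduled assessments".
- Efficacy values later than 28 days after the last dose are dropped.

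SAP 3.2.3 builds the OLE lipid time points from these weeks. At one year, "value at OLE Month 12 is defined as the average of OLE Week 50 (OLE Day 344) and OLE Week 52 (OLE Day 358) fasting" values. The first year-2 time point is built the same way: "value at OLE Month 15 is defined as the average of OLE Week 64 (OLE Day 442) and OLE Week 65 (OLE Day 449) fasting" values. Months 18 and 24 use OLE Weeks 77 and 78, and 102 and 104.

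SAP 1.1 provides for the second open-label year, "for a total of up to 2 years (104 weeks) of open label dosing following the 1 year (52 weeks) randomized phase".

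Appendix B lists 24 OLE lipid windows. Week 50 is 324 to 351 and Week 52 is Day 352 or later. Week 56 is 373 to 400, and the list runs on to Week 102 (688 to 715) and Week 104 (Day 716 or later).

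**The concern.** An open-ended last window is harmless when nothing follows it, as with the randomized-period Week 52 row. In the OLE list the same open limit sits in the middle, with 12 windows after it on the same day count. Every year-2 lipid value therefore satisfies two windows. The SAP gives no precedence between windows and does not close Week 52 for patients who keep dosing.

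At stake is the one-year OLE lipid summary. SAP 3.3 summarises fasting triglyceride descriptively at the 3.2.3 time points and at the Appendix B weeks. If the table is programmed as printed, OLE Week 52 and OLE Month 12 would no longer describe one year of open-label dosing for patients with year-2 data. The same values would also appear under their own weeks, which blurs any comparison of year 1 with year 2.

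**Working it through.** The point turns on intervals and weights. The plan states no figure to reproduce.

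**Inputs.** Target days and windows are from Appendix B, the clock and averaging rule from SAP 3.2.1, and the Month 12 definition from SAP 3.2.3.

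**1. Same clock.** The target day should equal (week − 1) × 7 + 1. Week 52 gives 51 × 7 + 1 = 358, Week 64 gives 63 × 7 + 1 = 442 and Week 104 gives 103 × 7 + 1 = 722. All 24 OLE target days satisfy this. Days 442 and 722 are the OLE days that SAP 3.2.3 gives for Weeks 64 and 104, so the year-2 rows count from the first OLE dose, as the year-1 rows do.

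**2. The rule behind the limits.** Each upper limit is the midpoint of adjacent target days, with halves rounded up:

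- Weeks 50 and 52: (344 + 358)/2 = 351; printed 351.
- Weeks 64 and 65: (442 + 449)/2 = 445.5, rounded to 446; printed 446.
- Weeks 102 and 104: (708 + 722)/2 = 715; printed 715.
- Weeks 52 and 56: (358 + 386)/2 = 372; no limit printed, but the next window opens at 373.

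Of the 23 boundaries between adjacent OLE windows, 22 follow the rule. Week 52/56 is the only exception.

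**3. Overlaps.** Comparing all pairs of the 24 windows gives exactly 12 overlaps. Each is Week 52 with one of Weeks 56, 60, 64, 65, 71, 77, 78, 84, 90, 96, 102 and 104.

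**4. Weight of year-2 values.** Assume one scheduled lipid value per target day, with the Week 52 visit itself present. With t year-2 values, the year-2 share of the Week 52 average is t/(t + 1). Month 12 is the mean of Weeks 50 and 52, so its share is half of that.

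| Year-2 values t | Share of OLE Week 52 | Share of OLE Month 12 |
|---|---|---|
| 1 | 1/2 = 50% | 25% |
| 6 | 6/7 = 85.7% | 42.9% |
| 12 | 12/13 = 92.3% | 46.2% |

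If Week 50 is missing, SAP 3.2.3 uses Week 52 alone, and the Month 12 share equals the Week 52 share.

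**5. After correction.** With Week 52 set to 352 to 372, the 24 windows have 0 overlaps and 0 gaps.

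**The case against.** **The intent is plain.** The SAP wants non-overlapping windows that collect values near a given week. A Day 722 value is not near Week 52, and the missing limit of 372 can be read from the row below. This stands as evidence that the open limit is an oversight, not a decision to pool two years. It does not settle what a program following the table would do, because no text says which window wins.

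**Sort by period first.** SAP 1.1 names separate OLE Year 1 and Year 2 periods, and an open last window works if records are split by year beforehand. The Study Period column of Appendix B does not come through cleanly in the text read here, so a separate year-2 label cannot be ruled out. But SAP 3.2.1 assigns values by OLE period, counted from the first OLE dose, with no split by year.

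**The 28-day limit.** It runs from the last dose, so it does not remove values taken while year-2 dosing continues.

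**The averaging sentence may cover only liver fat and HbA1c.** It follows a sentence about those two, though its wording is general. On the narrow reading, lipids have no rule for several values in a window and the overlap is still unresolved.

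**The impact is easily overstated.** This stands. A reader might infer that the whole OLE durability summary is wrong for every patient who stays beyond a year, or that efficacy conclusions are at risk. The documents support neither. The year-2 windows and Months 15, 18 and 24 still receive the right values. Only patients with a scheduled year-2 lipid value are touched. The triglyceride ANCOVA in SAP 3.3.2 uses randomized-period Months 3, 6 and 12 only.

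**Conclusion.** The defect holds as a contradiction between SAP 3.2.1 and Appendix B: one missing upper limit produces 12 overlapping pairs. Applied literally with the averaging rule, it puts year-2 values into OLE Week 52 and OLE Month 12 while also counting them in their own windows.

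The 12-of-13 figure is a ceiling. It assumes attendance at every year-2 lipid visit, one scheduled value per visit, and a program that follows the table and applies the averaging rule to lipids. SAP 3.1 and 3.8 state that study treatment was discontinued before the planned period ended, so the number of patients with year-2 data is unknown and may be small. The shares are weights, not bias: the shift in mean triglyceride depends on how far year-2 values differ from the one-year value, and the documents give no figure for that.

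The reach is narrow: two descriptive OLE lipid time points. No test changes. In the randomized period the same open limit precedes no later window, and the OLE Month 12 windows for liver MRI (to Day 418) and HbA1c (to Day 388) are closed. It is still worth correcting, because the rule as written gives a wrong summary and the repair is small.

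**What to change.** In Appendix B, change the OLE Week 52 lipid window to 352 to 372.

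One choice remains. For a patient whose last dose falls on OLE Day 358 at the end of year 1, on-treatment values are eligible up to Day 358 + 28 = 386. Those from Day 373 on would then fall in the Week 56 row. If the sponsor prefers to keep Day 352 and later for patients who stop at the end of OLE year 1, one added sentence should say so, with the existing limit of 28 days after the last dose applying.

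The cost is one table cell, plus that sentence if the exception is kept. No new data and no change to any model are needed.

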### **3.2.2 Patient Population Analyzed**

The following analysis sets will be used for the analysis of data as described within each analysis set.

**Full Analysis Set (FAS):** All patients who are randomized and received at least 1 dose of Study Drug in the randomized treatment period, and who have a baseline fasting triglyceride assessment (see definition in Section 3.2.3 for fasting lipid measurements). The FAS represents the practically-feasible intent-to-treat population as delineated in ICH Guideline E9.

Patients for whom the blind is broken during the trial will not be excluded from the FAS population. Patients will be analyzed in the treatment group to which they were randomized. Efficacy endpoint collected in both Randomized Treatment Period and OLE Period will be analyzed in FAS by the treatment group to which they were randomized. Although all patients receive volanesorsen during OLE period, assessment during OLE period will be analyzed according to the treatment assigned at previous Randomized Treatment Period. For example, if patient is assigned to the Placebo treatment at the Randomized Treatment Period, this patient will be analyzed in Placebo treatment group for both Randomized Treatment Period and OLE period.

**Safety Set 1 (SAF1):** All patients who are randomized and receive at least 1 dose of Study Drug (volanesorsen or Placebo) in the Randomized Treatment Period.

Patients will be analyzed in the actual treatment group patients received during the Randomized Treatment Period. Patients randomized to receive placebo, but incorrectly treated with volanesorsen will be counted in the volanesorsen group for the whole study period.

**Safety Set 2 (SAF2):** All patients who enter the OLE Period and receive at least 1 dose of Study Drug (volanesorsen) in the OLE Period.

As patients all receive volanesorsen in OLE period. In SAF 2, patients will be analyzed by the actual treatment received in the Randomized Treatment Period.

**PK Population:** All patients who are randomized, receive at least 1 dose of volanesorsen, and have at least one evaluable PK data, in either Randomized Treatment Period or OLE Period.

Patients will be analyzed in the actual treatment group patients received. Patients randomized to receive placebo, but incorrectly treated with volanesorsen will be counted in the volanesorsen group for the whole study period.

All primary, secondary [REDACTED] efficacy endpoints will be assessed in the FAS. Safety measures at Randomized Treatment Period and Randomized Treatment Period Post-Treatment Follow-up will be analyzed in SAF1. Safety assessment at OLE Period and OLE Post-Treatment Period will be analyzed in SAF2. PK endpoints will be assessed in the PK Population as applicable. Anti-drug antibody endpoints will be assessed in the SAF1.

Analysis populations will be summarized with counts and percentages by treatment group to which they were randomized, and overall.

### **3.2.3 Baseline and Endpoint Definition**

**The baseline for fasting lipid measurements** is defined as the average of Day 1 pre-dose assessment and the last non-missing measurement prior to Day 1 pre-dose assessment. If 1 of the 2 measurements is missing, then the other measurement will be assigned as the baseline value. If both are missing, then the baseline will be set as missing and the patient will be excluded from the FAS. Note that if on Day 1, there are multiple pre-dose assessments, then the last assessment with non-missing value will be used as the Day 1 pre-dose assessment.

**The baseline for other measurements** is defined as the last non-missing assessment prior to the first dose of Study Drug with the exception that platelet baseline is defined as the average of all assessments prior to the first dose of Study Drug.

Randomized Treatment Period and Open-Label Extension Period refer to one baseline, which is based on the pre-dose assessment of Day 1 in Randomized Treatment Period.

Efficacy by visit summary will include following time point, when data available. Both visit week and month will be presented.

**Randomized Treatment Period Month 3 analysis time point** is at the end of Randomized Treatment Period Month 3. For fasting lipid measurements, value at Month 3 is defined as the average of Week 12 (Day 78) and Week 13 (Day 85) fasting lipid measurements. If one visit is missing, then the other visit will be used. If both visits are missing, then the value will be set as missing

**Randomized Treatment Period Month 6 analysis time point** is at the end of Randomized Treatment Period Month 6. For fasting lipid assessments, value at Month 6 is defined as the average of Week 25 (Day 169) and Week 26 (Day 176) fasting assessments. If one visit is missing, then the other visit will be used. If both visits are missing, then value will be set as missing. .

**Randomized Treatment Period Month 12 analysis time point** is at the end of Randomized Treatment Period Month 12. For fasting lipid assessments, value at Month 12 is defined as the average of Week 50 (Day 344) and Week 52 (Day 358) fasting assessments. If one visit is missing, then the other visit will be used. If both visits are missing, then the value will be set as missing. .

**OLE Month 3 analysis time point** is at the end of OLE Month 3. For fasting lipid measurements, value at OLE Month 3 is defined as the average of OLE Week 12 (OLE Day 78) and OLE Week 13 (OLE Day 85) fasting lipid measurements. If one visit is missing, then the other visit will be used. If both visits are missing, then the value will be set as missing. .

**OLE Month 6 analysis time point** is at the end of OLE Month 6. For fasting lipid assessments, value at OLE Month 6 is defined as the average of OLE Week 25 (OLE Day 169) and OLE Week 26 (OLE Day 176) fasting assessments. If one visit is missing, then the other visit will be used. If both visits are missing, then value will be set as missing. .

**OLE Month 12 analysis time point** is at the end of OLE Month 12. For fasting lipid assessments, value at OLE Month 12 is defined as the average of OLE Week 50 (OLE Day 344) and OLE Week 52 (OLE Day 358) fasting assessments. If one visit is missing, then the other visit will be used. If both visits are missing, then the value will be set as missing. .

**OLE Month 15 analysis time point** is at the end of OLE Month 15. For fasting lipid assessments, value at OLE Month 15 is defined as the average of OLE Week 64 (OLE Day 442) and OLE Week 65 (OLE Day 449) fasting assessments. If one visit is missing, then the other visit will be used. If both visits are missing, then the value will be set as missing. .

**OLE Month 18 analysis time point** is at the end of OLE Month 18. For fasting lipid assessments, value at OLE Month 18 is defined as the average of OLE Week 77 (OLE Day 533) and OLE Week 78 (OLE Day 540) fasting assessments. If one visit is missing, then the other visit will be used. If both visits are missing, then the value will be set as missing. .

**OLE Month 24 analysis time point** is at the end of OLE Month 24. For fasting lipid assessments, value at OLE Month 24 is defined as the average of OLE Week 102 (OLE Day 708) and OLE Week 104 (OLE Day 722) fasting assessments. If one visit is missing, then the other visit will be used. If both visits are missing, then the value will be set as missing. .

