### **10.4 Definition of Baseline**

The baseline for fasting lipid measurements is defined as the average of Day 1 pre-dose assessment and the last measurement prior to Day 1. The baseline for other measurements is defined as the last non-missing assessment prior to the first dose of Study Drug.

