### ***3.4.2 Analysis of Secondary Endpoints***

#### ***3.4.2.1 Secondary Endpoint 1: Percent Change from Baseline in hepatic steatosis (as assessed by hepatic fat fraction using magnetic resonance imaging [MRI])***

Hepatic fat fraction (%), change from baseline, and percent change from baseline will be summarized by analysis visit using descriptive statistics in FAS. They will also be summarized separately by genetic mutation category: LMNA+PPARG, or neither. Descriptive summary statistics refers to section 3.2.1. Visit includes baseline and analysis visits according to the visit window defined in [Appendix B](#).

The percent change in Hepatic Fat Fraction (%) from Baseline to month 6 and month 12 at Randomized Treatment Period will be analyzed using the similar ANCOVA model as for the primary efficacy analysis model (ANCOVA).

A subgroup analysis of the ANCOVA will also be run for percent change in hepatic fat fraction in the group of genetically confirmed patients according to the University of Chicago data for patients who consented to genetic testing or historical data for patients who did not consent, and in patients with no mutation at month 6 and month 12 respectively.

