#### ***3.4.2.2 Secondary Endpoint 2: Change from Baseline in HbA1c***

HbA1c (%), change from baseline, and percent change from baseline will be summarized by analysis visit using descriptive statistics in FAS. They will also be summarized separately by genetic mutation category: LMNA, PPARG, or neither. Descriptive summary statistics refers to section 3.2.1. Visit includes baseline and analysis visits according to the visit window defined in [Appendix B](#).

The change in HbA1c from Baseline to Randomized Treatment Period month 3, month 6, month 9 and month 12 will be analyzed using this similar ANCOVA model as for the primary efficacy analysis

A subgroup analysis of the ANCOVA will also be run for change in HbA1c from baseline in the group of genetically confirmed patients according to the University of Chicago data for patients who consented to genetic testing or historical data for patients who did not consent, and in patients with no mutation at month 3, month 6, month 9 and month 12 respectively.

**3.4.2.3 Secondary Endpoint 3: Proportion of patients who achieve a >=40% reduction in fasting triglyceride from Baseline and >=30% reduction of hepatic fat fraction percent from baseline at Month 6**

Frequency and proportion of patients who achieve a >=40% reduction in fasting triglyceride from baseline and >=30% reduction of hepatic fat fraction from baseline at Month 6 will be displayed.

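### SAP Appendix B lets the hepatic fat fraction baseline window run to Study Day 14, while SAP 3.2.3 and protocol 10.4 require a value from before the first dose; the SAP does not say which rule prevails.

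*SAP*

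**What the plan says.** **Baseline rule.** Protocol 10.4: "The baseline for other measurements is defined as the last non-missing assessment prior to the first dose of Study Drug". SAP 3.2.3 repeats this for non-lipid measures (platelets excepted), for which baseline "is defined as the last non-missing assessment prior to the first dose of Study Drug", and adds that the randomized and open-label periods "refer to one baseline, which is based on the pre-dose assessment of Day 1 in Randomized Treatment Period".

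**Window rule.** SAP 3.2.1: "For the hepatic fat fraction and HbA1c data, data collected within the analysis visit window defined in" Appendix B will be used. For several values in one window, only scheduled ones count, and "the average will be used if there are multiple scheduled assessments". SAP 3.4.2.1, on HFF: "Visit includes baseline and analysis visits according to the visit window defined in" Appendix B.

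**The window.** Appendix B has one MRI row before Month 6. It is labelled Screening, with target day -42 to 1 and study-day window ≤ 14. The Month 6 window opens on Day 109.

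**Where the baseline is used.** The first secondary endpoint is "The percent change in Hepatic Fat Fraction (%) from Baseline to month 6 and month 12 at Randomized Treatment Period", analysed with an ANCOVA similar to the primary model (SAP 3.4.2.1). The composite in SAP 3.4.2.3 counts patients with a TG response and a ">=30% reduction of hepatic fat fraction from baseline at Month 6 will be displayed".

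**The concern.** A window ending on Day 14 extends past the first dose. With weekly dosing, the Day 1 and Day 8 injections both precede a Day 14 scan. If Appendix B is followed, a scan taken on treatment can serve as baseline. In the volanesorsen arm that value may already contain some drug effect; in the placebo arm it cannot. The baseline covariate would then be measured after randomization and could be affected by treatment.

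The analysed set also depends on the rule. A patient whose only early MRI falls on Days 2 to 14 has no baseline under SAP 3.2.3 and has one under Appendix B. HFF is the first-listed secondary endpoint and the only secondary endpoint with its own power statement, so its baseline should not be left to the programmer.

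**Working it through.** **1. The plan's own figure.** SAP 3.3.3 and protocol 10.2 state 92% power for a liver fat difference of 4.7 with SD 4, 20 versus 15 patients, two-sided alpha 0.05.

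- Standard error = 4 × √(1/20 + 1/15) = 1.366.
- Noncentrality = 4.7 / 1.366 = 3.44.
- Power = 91.6% by the noncentral t with 33 df, or 93.1% by the normal approximation.

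The stated 92% is reproduced. It does not depend on the baseline window, and the correction leaves it unchanged.

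**2. Pre-treatment rules side by side.**

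| Measure | Baseline in SAP 3.2.3 | Latest pre-treatment day in Appendix B |
|---|---|---|
| Lipids | Mean of Day 1 pre-dose and last earlier value | Day 1 |
| HbA1c | Last value before first dose | Day 1 |
| HFF | Last value before first dose | Day 14 |

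Only the HFF row passes Day 1. It exceeds its own target by 14 - 1 = 13 days.

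**3. Results under each rule.**

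| MRIs available early in the study | SAP 3.2.3 | Appendix B with SAP 3.2.1 |
|---|---|---|
| One pre-dose scan | That scan | Same |
| Pre-dose scheduled scan plus unscheduled scan on Days 2-14 | Pre-dose scan | Same, because only scheduled values count |
| Only a scan on Days 2-14 | No baseline; patient leaves the ANCOVA | Post-dose baseline; patient stays |
| Scheduled scans both before dosing and on Days 2-14 | Last pre-dose scan | Average of the two |

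The third row is where the conflict matters. The fourth needs a second scheduled MRI by Day 14, and protocol Appendix A appears to schedule only one before Month 6.

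**4. Direction of any bias.** Take an ANCOVA on change in HFF.

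- τ is the true treatment difference, negative for benefit.
- β is the slope of follow-up on baseline.
- q is the share of volanesorsen patients with a post-dose baseline.
- D is the mean drug-induced fall already present at that scan.

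Contamination lowers the volanesorsen baseline mean by qD, so the adjusted difference is approximately τ - β × (-qD) = τ + βqD. With β and D positive, this is closer to zero than τ. Percent change has no such simple identity, but a lower baseline denominator also makes a given follow-up value look like a smaller fall. The documents give no value for q, D or β, so the shift cannot be quantified.

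**5. Effect on the composite, for an assumed patient.** Suppose HFF falls from 20% pre-dose to 13.6% at Month 6. The true reduction is 6.4/20 = 32%, which meets the HFF criterion. If a share g of the fall is already in the baseline, the apparent reduction is 1 - 13.6/(20 - 6.4g).

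| Assumed g | Baseline used | Apparent reduction |
|---|---|---|
| 13/175 = 7.4% (linear fall, Day 14 scan, Month 6 scan on Day 176) | 19.52 | 30.3% |
| 15% | 19.04 | 28.6% |
| 25% | 18.40 | 26.1% |

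A patient near the 30% threshold can change category. The table shows the mechanism and does not estimate how often this happens.

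**The case against.** The strongest reply is that SAP 3.2.3 already settles the baseline and Appendix B does not redefine it. The MRI row is labelled Screening, not baseline. For lipids, Appendix B lists separate Screening, Qualification and Day 1 rows while the baseline is the average in 3.2.3, so its rows are not baseline rules in general. SAP 3.3 makes that division for triglycerides: baseline and endpoint from 3.2.3, analysis weeks from Appendix B. The HFF sentence in 3.2.1 follows the rule for mapping early-termination visits, which suggests that it concerns post-baseline data.

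This stands in part: 3.2.3 read alone gives the right baseline. But 3.4.2.1 names baseline together with the analysis visits when it points to Appendix B, and no other MRI row could supply one.

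The limit may also be a typing error. That is possible, but it does not correct itself. A restored minus sign (≤ -14) would exclude Days -13 to 1, which lie inside the row's own target.

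The reply on practical reach largely stands. Inclusion criterion 6 requires a Screening MRI with HFF of at least 6.4%. Protocol 4.2 places randomization after all screening assessments. Footnote a of the placebo-controlled schedule puts MRI collection in the diet stabilization period.

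A reader might infer that late MRIs were more common before Amendment 4 added criterion 6. The amendment log shows only that the criterion was added, not that earlier scans were done after dosing. MRI-assessed steatosis was already a secondary endpoint.

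**Conclusion.** The conflict is real, in current text, and narrow. For an MRI on Days 2 to 14, SAP 3.2.3 and Appendix B give different answers, and the SAP does not rank them. This affects the analysed set and the baseline covariate for the first secondary endpoint. Any bias is likely toward no effect, assuming that liver fat has begun to fall on drug by the scan and that follow-up correlates positively with baseline. The reach is probably small.

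Three stronger readings are not supported:

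- **A post-dose MRI will be the baseline.** It becomes one only if Appendix B is applied over 3.2.3 and a late scan exists.
- **Pre-dose and post-dose values will be averaged.** No second scheduled MRI by Day 14 appears in the protocol schedule.
- **Power falls by a stated amount.** The number of late scans and the onset of the HFF effect are not given. The 4.7 and SD 4 read as absolute fat-fraction points, while the SAP's ANCOVA is on percent change.

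The composite is affected only as a reported proportion, because SAP 3.4.2.3 and 3.8 make it descriptive.

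**What to change.** In SAP Appendix B, end the HFF Screening window at Day 1 pre-dose. Add one sentence to 3.2.1 or 3.4.2.1: the HFF baseline follows 3.2.3, is the last pre-dose MRI, and is not averaged. An MRI first done on Days 2 to 14 is then not used as baseline in the main ANCOVA or the composite; a sensitivity analysis may include it. Make the change before the HFF dataset is derived, so that the choice does not depend on the results.

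The cost is one table cell and one sentence, and no stated figure changes. The downside is that any patient with only a Day 2 to 14 MRI leaves the main HFF analysis. The number of such patients should be reported.
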